11.1 Protection of subject privacy	

	11.2 informed consent	.37
	11.3 Approval of the ethics committee	. 37
	11.4 Declaration of Helsinki	. 38
12	Quality control and quality assurance	.38
13	Study termination	38

1 Summary of the clinical trial protocol

Research name	Effect of adding breast milk oligosaccharides and multinutrient optimized infant formula on the growth and development of infants aged 0 to 1 years: a multicenter, double-blind, randomized, controlled trial			
research design	Multicenter, randomized, controlled, parallel, double-blind trial			
sample capacity	240			
Interventio n cycle	360 Days			
purpose of research	Compare add milk oligosaccharides and a variety of nutrients optimization of infant formula and conventional infant formula on the immune function of infants under 1 year of age, and compared with breastfeeding infants, explore different infant formula on infant intestinal health, immune function, growth and development, cognitive development and tolerance.			
Main end point	Intestinal indicators (16s r RNA, SCFAs)			
Secondary end point	 Inflammation indicators: serum hsCRP; Nutritional index: serum albumin; Immune indicators: fecal sIgA and blood lymphocyte subsets; Growth and development indicators: height, weight, head circumference and chest circumference; Bone development indicators: osteocalcin, alkaline phosphatase; Tolerance indicators: survey of infant gastrointestinal comfort, infant sleep crying, infant diarrhea and upper respiratory tract infection, infant stool Bristol stool classification; Cognitive development: Bailey Infant Development Scale (version 			

	IV), serum amino acids.					
Safety indicators	• Adverse events and serious adverse events.					
	Inclusion criteria for the breast-feeding group:					
	\cdot The 0 ~ 28 days after birth;					
	· Single-child birth;					
	• The gestational age was from 37 to 42 weeks;					
	\cdot Birth weight is 2500 ~ 4000 g;					
	• Parents or guardians agree to exclude the infant from participating in other interventional clinical studies during this study;					
	• Parents or guardians agreed to feed the baby according to the trial protocol;					
Inclusion	Inclusion criteria for the artificial feeding group:					
criteria	\cdot The 0 ~ 28 days after birth;					
	· Single-child birth;					
	• The gestational age was from 37 to 42 weeks;					
	\cdot Birth weight is 2500 ~ 4000 g;					
	• Parents or guardians agree to exclude the infant from participating in other interventional clinical studies during this study;					
	• Parents or guardians agreed to feed the baby according to the trial protocol;					
	• The mothers cannot be exclusively breastfeeding due to subjective and objective reasons.					
	· Artificial assisted reproduction;					
Exclusion criteria	• The mother suffers from diseases that may endanger the intrauterine growth;					
	• The mother had gestational diabetes mellitus or severe metabolic disease or chronic disease at the time of pregnancy;					
	· Having congenital malformations and genetic, chronic, and					

	congenital diseases that may interfere with the investigation;				
	• IgE mediated milk protein allergy or factors that increase the risk of milk protein allergy;				
	· Having an acute infection or gastroenteritis;				
	· Functional gastrointestinal diseases, such as gastroparesis;				
	· Is participating in other clinical trials;				
	• The investigator was unable to determine the parents' willingness or ability to comply with the protocol requirements.				
	• Ineligible (ignored during screening, occurred during the study or found by review);				
	Serious protocol deviation occurs;				
	• Serious non to protocol or test requirements;				
Exit standard	• Need to terminate the designated formula due to adverse events or cause failure to continue following the trial procedures;				
	• Need to discontinue the designated formula or cause the inability to follow the trial procedures due to disease progression;				
	• Withdraw informed consent or remove informed consent;				
	• Misvisit.				
	Test group: Artificial feeding of the experimental formula				
	0-4 months of age: artificial feeding is not less than 2 times a day;				
	4~12 months of age: artificial feeding is not less than 5 times a day;				
Interventio	Control group: artificial feeding of the control formula				
n method	0-4 months of age: artificial feeding is not less than 2 times a day;				
	4~12 months of age: artificial feeding is not less than 5 times a day;				
	Breastfeeding group: breastfeeding				
	0-4 months of age: exclusive breastfeeding (must be fully				

	breastfeeding 1 day before the visit)					
	4 to 12 months old: breastfeeding at least once a day					
	In the artificial feeding group, 160 infants from 0 to 28 days were randomly divided into trial group and control group, 80 infants in each group; 80 breastfed infants were included in the same period. The test group, control group and breastfeeding group were fed the infants. Based on the time of the last visit, the visit was conducted at $28,90 \pm 3$ days, 180 ± 5 days and 360 ± 7 days after birth.					
	metric	dressing by screenin g	Visit 1 (28 Days)	Visit 2 (90 Days)	Visit 3 (180 Days)	Visit 4 (360 Days)
	Demographic data	\checkmark	\checkmark			
	Bailey Infant Development Scale (Version IV)					V
Research implementa tion	Growth and development indicators		\checkmark	\checkmark	V	\checkmark
	excrement and urine 16S rRNA SCFAs sIgA 		V		V	N
	blood · hsCRP • Lymphocyte subsets • amino acid · bone gla protein · alkaline phosphatase				V	N

· albumin				
Feeding status, Intake questionnaire (breastfeeding and formula feeding)	\checkmark	\checkmark	V	\checkmark
Gastrointestinal comfort questionnaire	\checkmark	\checkmark	\checkmark	\checkmark
Sleep crying questionnaire	\checkmark	\checkmark	\checkmark	\checkmark
Questionnaire for diarrhea and upper respiratory tract infections	\checkmark	\checkmark	V	\checkmark
Bristol Stool Classification	\checkmark	\checkmark	\checkmark	\checkmark

2 research background

Breast milk is widely recognized as the most perfect food for the newborn period. Breast milk naturally contains the best proportion of various nutrients suitable for the baby's digestion and absorption^{[,]12}, Such as protein, fats, carbohydrates, vitamins, and minerals. In addition, breast milk also contains a variety of bioactive ingredients suitable for infants, such as lactoferrin, immunoglobulin, hormones, oligosaccharides, probiotics and so on^{[,]34}, These bioactive ingredients play an important role in the health of infants and young children.

⁷ Vos, A.P.; Haarman, M.; Buco, A.A specific prebiotic oligosaccharide mixture stimulates delayed-type hypersensitivity in a murine influenza vaccination model.Int.Immunopharmacol.2006, 6, 1277–1286.

⁸ Espinosa, R.M.; Tamez, M.; Prieto, P.Efforts to emulate human milk oligosaccharides.Br.J.Nutr.2007, 98, 74–79.

hexasaccharide (lacto-N-hexaose, LNH) and other core structures. The structure of FOS and GOS is simpler, and the addition of FOS and GOS in formula is considered a relatively reasonable and cheap scheme to simulate breast milk. The difference between these two and HMOs in breast milk still need more research to demonstrate. The 2 '-fucinose-based lactose (2' FL) and LNnT have been used in infant formula. Some studies showed that supplementing 2 ' -FL (1 g / L) and LNnT (0.5 g / L) on the basis of formula, the intestinal flora of infants at 3 months contained more bifidobacterium and less Echia, digestive Streptococcus, closer to that of breast-fed infants; the content of important metabolites such as propionate, butyrate and lactate in feces of infants where HMOs were supplements^{[,]910}.

HMOs are capable of blocking the adhesion of pathogens. Many viruses or bacteria must attach to the surface of epithelial cells to proliferate and cause disease, and HMOs act as soluble ligands like blocking adhesion to pathogens. Animal experiments showed that 2 ' FL reduced the invasion of Chlamydia jejunae by 80% and inhibited the release of mucosal pro-inflammatory signals, which subsequently reduced the number of episodes of diarrhea. LNnT was shown to reduce the number of S. pneumoniae cells in the lungs of an animal model^{[]11}. The anti-adhesive properties of HMOs also apply for dissolution. Entamoeba, and histolytica, capable of destroying epithelial cells of the large intestine, liver, lung or spleen, is regarded as the third leading cause of parasite death worldwide^{[]12}. Entamoeba histolytica needs to be attached to the colon mucosa of the host, and endohistolytica will be excreted with the feces and will not cause disease.

prebiotics to formula. HMOs are not destroyed by the gastric acid of the human body, nor decomposed by digestive enzymes, and can directly reach the large intestine, stimulate the growth of beneficial bacteria (bifidobacteria and Lactobacillus) in the intestinal tract, indirectly inhibit the growth of harmful bacteria, and maintain the balance of intestinal microecology. Therefore, HMOs are regarded as the primary prebiotics (prebiotics) of human beings^{[]13}. Bifidobacterium in the large intestine can produce acetic acid, propionate and butyric acid through fermentation, acetic acid can reduce the pH value in the intestinal tract and inhibit the growth of pathogenic bacteria; propionate and butyrate have important physiological functions; butyrate is an important energy source for colon cells. HMOs are able to indirectly increase the production of short-chain fatty acids (SCFA s), and most SCFAs are rapidly absorbed by colonic cells or used as energy sources^{[]14}. Research evidence suggests that SCFAs are able to participate in the regulation of gene expression^{[]15}, Play an important role in the activation and differentiation of immune cells and is associated with inflammatory and allergic diseases^{[,]1617}.

HMOs are able to provide protection against multiple viruses^{[.,]181920}. HMOs promote the maturation of the immune system, produce a more balanced Th 1 / Th 2 cytokine response; stimulate the immune response and maturation of epithelial cells to protect the host from viral infection; affect the diversity and concentration of the microbiome and stimulate the growth of commensal bacteria. Another antiviral activity of HMOs is based on structural similarity to the glycochains of glycoconjugates present on the epithelial surface, mimicking the surface glycans of epithelial cells, and in turn capturing viruses that do not adhere to the cells. Virus lectin receptors blocked by HMOs fail to participate in recognizing the glycosites

¹³ REID G.Probiotics and prebiotics-progress and challenges[J].International Dairy Journal, 2008, 18(10/11): 969-975. DOI:10.1016/j.idairyj.2007.11.025.

¹⁴ Kulinich, A.; Liu, L.Human milk oligosaccharides: The role in the fine-tuning of innate immune responses.Carbohydr.Res.2016, 432, 62–70.

¹⁵ Koh, A.; De Vadder, F.; Kovatcheva-Datchary, P.; Backhed, F.From Dietary Fiber to Host Physiology: Short-Chain Fatty Acids as Key Bacterial Metabolites.Cell 2016, 165, 1332–1345.

HMOs are able to promote immune function development in infants. In the first 6 months of life, breastfeeding was shown to promote the maturation of the immune system, feeding enough to reduce the incidence of many diseases such as asthma, allergies, inflammatory bowel disease, type 1 diabetes, celiac disease, and leukemia. HMOs are very important components in breast milk and can affect the infant immune system through multiple mechanisms including blocking pathogen adhesion and promoting bifidobacterium colonization. The composition of the infant gut flora and epithelial cell responses mediated by HMOs may indirectly affect the infant's immune system. In vitro studies have shown that HMOs can also directly modulate the immune response. The HMOs may act locally on the lymphohistiocytes associated with the mucosa^{[,]2122}. Many immune receptors recognize the oligosaccharide structures of their glycoprotein ligands. HMOs are structurally similar to ligand, thus it is speculated that they may bind directly to immune cells^{[,]2324}, This binding can cause signaling, leading to changes in the nature and function of immune cells.

HMOs can reduce the risk and mortality of necrotizing enterocolitis (NEC). NEC causes severe and fatal destruction of the gut in infants, with more than 25% of NEC babies dying, and surviving infants often have long-term neurological complications. The risks of NEC were 6 to 10 times lower than formula-fed infants^{[,]2526}. Animal experiments in rat models showed that HMOs prevent the release of NEC. If these results are translated into NEC in humans, lactose disialate-N-tetrasaccharide (DSLNT) can be used to prevent or treat NEC in formula-fed infants, and its concentration in breast milk can be used as a biomarker to identify the risk of breast-

²¹ Macpherson, A.J.; Geuking, M.B.; McCoy, K.D.Immune responses that adapt the intestinal mucosa to commensal intestinal bacteria.Immunology 2005, 115, 153–162.

²² Goehring, K.C.; Kennedy, A.D.; Prieto, P.A.; Buck, R.H.Direct evidence for the presence of human milk oligosaccharides in the circulation of breastfed infants.

²³ Eiwegger, T.; Stahl, B.; Haidl, P.; Schmitt, J.; Boehm, G.; Dehlink, E.; Urbanek, R.; Szepfalusi, Z.Prebiotic oligosaccharides: In vitro evidence for gastrointestinal epithelial transfer and immunomodulatory properties.Pediatr.Allergy Immunol.2010, 21, 1179–1188.

different degrees of antibacterial effect, with broad spectrum antibacterial, it may benefit from the following mechanism: (1) the antibacterial properties of lactoferrin from its high iron binding ability, and the growth process of bacteria also need a lot of iron, lactoferrin can compete and inhibit the use of iron source, achieve the purpose of antibacterial^{[]38}. (2) for gram-negative bacteria, lactoferrin by positive amino acid group and bacterial outer membrane anionic lipopolysaccharide (LPS), can inhibit LPS and other cations (such as Ca 2 +, Mg2 +, etc.), and cause LPS from the cell wall, bacterial cell wall permeability increase, bacterial cell apoptosis, achieve the effect of antibacterial, research also proved that the interaction of lactoferrin and LPS can also enhance natural antibacterial agents (such as lysozyme) antibacterial^{[,,]394041}. (3) For Gram-positive bacteria, the positive group of lactoferrin can react with the negative charge brought by the anionic material lipoteichoic acid on the surface of the bacteria, thus reducing the negative charge of the cell wall, leading to the reaction of lysozyme and the underlying peptidoglycan, and playing the inhibitory role of lysozyme^{[]42}.

Recent studies have found that lactoferrin has antiviral ability, which may be achieved through the following ways: (1) lactoferrin interferes with the viral replication and syncytial process to inhibit the activity of the virus. In vitro results show that lactoferrin inhibits viral replication in host cells in human plasma and milk, thereby inhibiting AIDS (AIDS) viral activity^{[]43}. (2) Lactoferrin can inhibit the entry of viral particles into the host cells by either directly attaching to the virus or by blocking its cellular receptors. The results show that lactoferrin can interfere with the transmission of human immunodeficiency virus (HIV-1), blocking its transmission from dendritic cells to TCD 4 cells by blocking the binding of the virus to epithelial cellshand over^{[]44}.

Moreover, lactoferrin can play an immunomodulatory role by acting on immune

³⁸ Chilton C H, Crowther G S, Spiewak K, et al.Potential of lactoferrin to prevent antibiotic-induced Clostridium difficile infection[J].Journal ofAntimicrobial Chemotherapy, 2016, 71(4): 975-985.

³⁹ Di Wei, Jin Haizhu, Du Ming, et al. Status and prospects of lactoferrin research [J]. Jiangxi Journal of Agriculture, 2012,24 (3): 167-169,175.

2.3 Docosahexaenoic acid and eicosapentetraenoic acid

Docosahexaenoic acid and eicosapentetracenoic acid is two important long chain polyunsaturated fatty acid (LCPUFA), referred to as DHA and ARA, can be the precursor fatty acid α -linolenic acid (ALA) and linoleic acid (LA) in the body, the two is not only constitute two main fatty acids of brain phospholipids, or the central nervous system development essential nutrients, DHA accounted for 10% of the brain. It is known that the critical period of brain development is from the beginning of pregnancy to the second 2 years of birth. During this critical period of development, brain cells develop and differentiate rapidly, and are extremely sensitive to internal and external environment changes and stimulation. Dobbing Sands showed that the weight of the brain increased from about 20g in the second to third months of life to

⁴⁵ Artym J, Zimecki M, Kruzel M L.Reconstitution of the cellular immune response by lactoferrin in

cyclophosphamide-treated mice is correlated with renewal of T cell compartment[J].Immunobiology, 2003, 207(3): 197-205.

⁴⁶ Shau H, Kim A, Golub S H.Modulation of natural killer and lymphokine activated killer cell cytotoxicity by lactoferrin[J].J Leukoc Biol, 1992, 51(2):343-349.

⁴⁷ Drago-Serrano ME, de la Garza-Amaya M, Luna JS, et al.Lactoferrin-lipopolysaccharide(LPS) binding as key to antibacterial and antiendotoxiceffects[J].Int Immunopharmacol, 2012, 12(1): 1.

⁴⁸ Puddu P, Valenti P, Gessani S.Immunomodulatory effects of lactoferrin on antigen presenting cells[J].Biochimie, 2009, 91(1): 11-18.

about 1200g at 2 years^{[]49}. Martinez et al reported a nearly 30-fold increase in DHA and ARA content in infant brains from birth to 2 $y^{[,]5051}$. This also reflects the importance of DHA and ARA in the growth and development of infants and young children.

Although fetuses and newborns can also synthesize DHA and ARA by themselves, these long-chain polyunsaturated fatty acids are not able to meet the needs of rapid growth^{[]52}. Therefore, early in life growth and development, breast milk and or breast milk substitutes are the main food sources for DHA and ARA. Brenna The team analyzed 106 breast milk studies, which selected 65 studies with a total sample size of 2474 women and found that the mean content of DHA ($\% \pm$ standard deviation) was $0.32 \pm 0.22\%$ total fatty acids (range: 0.06~1.4%) and ARA was 0.47 ± 0.13% total fatty acids (range: 0.24-1.0%). DHA is less abundant in breast milk than ARA and more different than ARA. In addition, the results found that the coastal population had the highest DHA content and was associated with more dietary intake of seafood, and the lowest DHA content occurred in inland populations and developed countries, which was associated with low fish intake^{[]53}. Yuhas et al collected 440 breast milk samples from Australia, Canada, Chile, China, Japan, Mexico, Philippines, the United States and showed that DHA ranged from 0.17 wt% to 0.99 wt%, the highest value was Japan, the lowest value was samples from Canada and the United States, and the average DHA content of samples from China was 0.83%. The content of ARA was stable in several studied countries, from 0.36wt%~0.49wt%, the mean was 0.41%. The result in China was 0.49% total fatty acids. The mean \pm standard deviation of the absolute content of Chinese DHA is 149.8 ± 10.5 mg/L, and the mean \pm standard deviation of the absolute content of ARA was 207.8 \pm 12.05 mg / $L^{[]54}.$ Koletzko B Led his team to review LCPUFA during pregnancy, lactation and infancy, and showed that the overall average of ARA in breast milk ranged from 0.35% to 0.70% total fatty acids, and the overall mean of DHA ranged from 0.17% to 1.0% total fatty acids. Based on the results of the literature study, it is recommended that the amount of DHA is 0.2 to 0.5%, and the minimum amount of ARA should not be lower

⁴⁹ Dobbing J, Sands J, Quantitative growth and development of human brain[J].Arch.Dis.Child, 1973, 48:757-767.

⁵⁰ Martinez M, Tissue levels of polyunsaturated fatty acids during early human development [J].J Pediatr.1992, 120(4):S129-38.

⁵¹ Martinez M, Mougan I, Fatty acid composition of human brain phospholipids during normal development [J].J.Neurochem.1998, 71:2528-2533.

3.4 Bifidobacterium long long subspecies BB536

Bifidobacterium BB536 isolated the intestines of healthy infants in 1969 and has been approved for infant food in Japan and the United States. It is the first affinity human Bifidobacterium strain (HRB) recognized by the US FDA. At the same time, in 2022, it was approved to be included in China's list of edible fungus list.

As of March 2022, more than 220 academic papers were published based on BB536. A number of clinical studies on infants at home and abroad have proved that the strain has good food safety. Studies have proved that BB536 is effective in maintaining intestinal health, improving immunity, and preventing infection.

3 Study purpose and significance

To compare the effects of breast milk oligosaccharide and multinutrientoptimized infant formula and conventional infant formula on the intestinal health of infants under 1 year of age. In comparison with breast-fed infants, the effects of different infant formulas on infant growth and development, cognitive development, immune function, intestinal comfort, crying, and upper respiratory tract infection were explored.

4 research contents

This trial is a multicenter, randomized, controlled, parallel, double-blind, exploratory trial to compare the effects of infant formula, conventional infant formula on infant formula and breast milk in early life.

240 subjects are expected to be required for this trial. From 0 to 28 days after birth, infants who had signed informed consent by a guardian were screened. Guardian according to their own will choose to attend breastfeeding group or artificial feeding group (mother for subjective and objective reasons for exclusive breastfeeding, can choose to join artificial feeding group, the researchers shall not interfere in the decision of the guardian or guide), breast feeding group and artificial feeding group subjects of 80 cases and 160 cases, respectively.160 subjects in the artificial feeding group were randomly assigned to the experimental group and the control group in a ratio of 1:1 ratio. The experimental formula and control formula were used for artificial feeding or mixed feeding. Artificial feeding was conducted no less than 2 times a day at 0 to 4 months and no less than 5 times a day at 4 to 12 months. Infants in the breastfeeding group need to be breastfed or mixed fed, exclusively breastfeeding daily at 0 to 4 months of age (must be fully breastfed 1 day before the visit), and breastfeeding at least once a day at 4 to 12 months of age.

From the perspective of ethical and subject protection, if the infant and guardian

are eligible and willing to breastfeeding, we will assign the subject to the breastfed group, rather than against the wishes of the parent. If the parent / legal guardian is unable to breastfeed exclusively for objective reasons, or clearly and strongly willing not to breast, these infants will be randomized to the trial or the control group. It should be noted that during the decision-making process, the investigator should encourage the parents / guardian to breastfeeding the infant; rather than interfering or guiding the decision-making process to induce the test infant to participate in the artificial feeding group.

Visit 1 will be performed on the 28th day after birth and the intervention period will last 332 days (slightly changed by clinic visit time) consisting of 3 visits: Visit 2 (90 ± 3 days after birth), Visit 3 (180 ± 5 days after birth), and Visit 4 (360 ± 7 days after birth). Subjects in each group will be enrolled 1:1 and based on an expected completion rate of 80%, 64 subjects are expected to complete the trial. Participants who withdrew from the study before Visit 4, failed in three contacts, met the withdrawal criteria, seriously violated the trial protocol, or met other withdrawal criteria were excluded by the investigators.

In addition, indicators and incidence of adverse events (e. g. eczema) will be recorded and compared during the study. For the purposes of this trial, adverse events were defined as any adverse and unexpected signs (including other abnormal laboratory results beyond the study plan), symptoms, disease related to participation in the clinical trial, and the disease related to the trial product.

5 subject investigated

Infants born 0 to 28 days after birth are screened and who meet all inclusion criteria and do not meet any exclusion criteria will be assigned to the breastfeeding group or randomized to the trial / control group.

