6.1 Test flow chart

6.2 recruit

The investigator will identify suitable infants, contact their parents or guardians by telephone and otherwise, and make an appointment for informed consent and subject screening.

6.3 informed consent

The subject's guardian must personally sign the informed consent form and date before conducting any trial process. If the version is updated, contact the guardian to sign the latest version of the informed consent.

A written version of the informed consent was provided to the guardian of the subject, and the investigator should explain the following: the nature of the trial; the content of the subject; the requirements of the protocol; known side effects and any risks involved in participation. The guardian should also be clearly informed that the baby can be withdrawn from the study at any time for any reason, without affecting the baby's medical treatment, legal rights, and no obligation to provide a reason for the withdrawal.

The guardian of the subject was allowed enough time to consider the relevant information and the opportunity to ask the researcher, their GP or other independent party to decide whether to enroll the infant in the trial. The subject's guardian will then sign and date the informed consent form, followed by the investigator giving the informed consent. The investigator who gave the informed consent must have the appropriate qualifications and experience and must be authorized by the principal investigator at each institution. A copy of the signed informed consent form will be given to the subject's guardian for retention and the original remains at the study institution.

6.4 dressing by screening

The investigator will ask the guardian, investigate the basic information of the subject infant, fill in the screening record and the Subject Screening and Enrollment Registration Form, and the infant will be included in the study after meeting the inclusion and exclusion criteria. If the guardian chooses to exclusively breastfeed the infant, the infant will be assigned to the breastfeeding group; if due chooses artificial or mixed feeding, the infant will be randomized to the trial or control group.

6.5 randomization

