6.5.1 Random group table

Randtrial block randomization. The randomization tables were generated simulated on a computer by an unblinded statistician using the SAS software according to the random number table. Trial or control milk powder were coded according to the randomization table. Each center will compete for entry. In clinical operation, the authorized investigator or the research assistant will distribute the test or control milk powder according to Powder No. Any deviations should be truthfully recorded for evaluation before data analysis.

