6.6 Interview

6.6.1 Visit 1

Visit 1 will be performed on the 28th day of life and the investigator will obtain the following information:

· Mode of delivery;

· Pregnancy-related complications;

· Parents' physical condition (height, weight, medical history);

· Parents' living habits (smoking history, drinking history, exercise habits);

· Parents' social and economic background (education level, employment status);

· Growth and development parameters (height, head circumference, chest circumference, body weight);

- Stool samples (16S rRNA, SCFAs, sIgA);
- · Gastrointestinal comfort survey and questionnaire;
- · Questionnaire on baby crying condition;
- · Questionnaire on infant diarrhea;
- · Questionnaire on upper respiratory tract infection in infants;

⁵⁷Steenhout P, Sperisen P, Martin F, et al.Term Infant Formula Supplemented with Human Milk Oligosaccharides (2' Fucosyllactose and Lacto - N - neotetraose) Shifts Stool Microbiota and Metabolic Signatures Closer to that of Breastfed Infants[J].The FASEB Journal, 2016, 30.

- · The Bristol Stool Classification Questionnaire;
- · Past medical history and current medical history.

6.6.2 Visit 2

Visit 2 will be conducted on Birth Day 90 with a window of 3 days and the investigator will measure and obtain the following information:

· Growth and development parameters (height, head circumference, chest circumference, body weight);

- · Gastrointestinal comfort survey and questionnaire;
- · Questionnaire on baby crying condition;
- · Questionnaire on infant diarrhea;
- · Questionnaire on upper respiratory tract infection in infants;
- · The Bristol Stool Classification Questionnaire;
- · Adverse events and serious adverse events.

6.6.3 Visit 3

Visit 3 will be conducted on Post Birth Day 180 with a window of 5 days and the investigator will measure and obtain the following information:

· Growth and development parameters (height, head circumference, chest circumference, body weight);

- Blood samples (hsCRP, analysis of lymphocyte subsets, amino acids, osteocalcin, alkaline phosphatase, albumin);
- Stool samples (16S rRNA, SCFAs, sIgA);
- · Gastrointestinal comfort survey and questionnaire;
- · Questionnaire on baby crying condition;
- · Questionnaire on infant diarrhea;
- · Questionnaire on upper respiratory tract infection in infants;
- · The Bristol Stool Classification Questionnaire;
- · Adverse events and serious adverse events.

6.6.4 Visit 4

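### The synopsis gives a 360-day intervention and Section 4 gives 332 days; no text places the first study feed after the Visit 1 stool, so its use as a baseline is not secured

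*Protocol*

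**What the plan says.** The protocol gives two durations. The synopsis (Section 1) lists an intervention cycle of 360 days. Section 4 states: "Visit 1 will be performed on the 28th day after birth and the intervention period will last 332 days". It qualifies this as "slightly changed by clinic visit time" and says the period is made up of Visits 2, 3 and 4.

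On when study powder begins, the text points two ways.

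- Towards a start at Visit 1: Section 4 as quoted, and the visit lists in 6.6. Visit 1 collects delivery mode, parental background and medical history. "Adverse events and serious adverse events" appears in the lists for Visits 2 to 4 but not for Visit 1.
- Leaving an earlier start open: the synopsis says "160 infants from 0 to 28 days were randomly divided into trial group and control group". Section 6.4 says, as part of screening, that "the infant will be randomized to the trial or control group". The feeding minimum in the synopsis reads "0-4 months of age: artificial feeding is not less than 2 times a day", and Section 4 repeats it: "Artificial feeding was conducted no less than 2 times a day at 0 to 4 months". Section 7.1 has a first test formulation for 0–3 months. Section 6.5.1 says that staff "will distribute the test or control milk powder according to Powder No", with no visit named.

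Stool for 16S rRNA and SCFAs, the primary endpoint in 8.1, is collected at Visits 1, 3 and 4. Section 9.7.1 words the primary endpoint as changes in intestinal flora, test against control. Section 9.7.2 describes between-group rank tests and does not say that the Visit 1 value is subtracted or adjusted for.

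**The concern.** Two durations 28 days apart imply two different starting points for study feeding. The starting point decides what the Visit 1 stool is. If powder begins at Visit 1 after sampling, the stool is a pre-exposure baseline. If powder begins at enrolment, it is an early on-treatment sample, taken after a different number of days of study formula in each infant.

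This matters because the primary endpoint is worded as a change, and Visit 1 is the only stool that could anchor one. In a multicentre trial, two sites could each follow the text and start powder up to 28 days apart. The order of stool and first feed cannot be repaired once the samples have been taken.

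**Working it through.** Inputs, all from the protocol:

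- Synopsis duration: 360 days.
- Section 4 duration: 332 days.
- Visit 1: day 28. Visit 3: day 180 ± 5. Visit 4: day 360 ± 7.
- Age at randomisation: 0–28 days.

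**1. Reproduce the Section 4 figure.** Nominal Visit 4 minus Visit 1: 360 − 28 = 332. This matches exactly.

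**2. Can the visit window explain 360?** With a day-28 start, the earliest Visit 4 gives 353 − 28 = 325 days and the latest gives 367 − 28 = 339. The value 360 lies outside 325–339. To reach it from day 28, Visit 4 would have to fall on day 28 + 360 = 388, which is 21 days past the window.

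**3. What start does 360 require?** At the nominal Visit 4, 360 − 360 = day 0, that is, birth. At the latest permitted Visit 4, 367 − 360 = day 7. Neither is compatible with a start at Visit 1.

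**4. Exposure under each reading.** For a start on day d, exposure at a visit on day v is v − d. Under a Visit 1 start, d = 28. Under an enrolment start, d runs from 0 to 28.

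| Visit | Start at Visit 1 | Start at enrolment |
|---|---|---|
| Visit 1 (day 28) | 0 days | 0–28 days |
| Visit 3 (day 180) | 152 days | 152–180 days |
| Visit 3 with window (175–185) | 147–157 days | 147–185 days |
| Visit 4 (day 360) | 332 days | 332–360 days |
| Visit 4 with window (353–367) | 325–339 days | 325–367 days |

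**5. Effect on the analysis.** Randomisation balances the two formula arms at allocation. A direct comparison at day 180 or day 360 is therefore valid whether powder began at Visit 1 or at enrolment; only the length of exposure being compared differs. A comparison that uses the Visit 1 stool as a baseline is different. It has its intended meaning only if that stool precedes study formula, which the protocol implies but does not require.

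**The case against.** The strongest reply is that Section 4 nearly settles the matter. It puts Visit 1 on day 28, counts only Visits 2 to 4 within the intervention, and gives a duration that equals 360 − 28 to the day. The content of Visit 1 is that of a baseline visit, and adverse events are collected only afterwards. The synopsis figure is most simply the infant's age at the last visit. The statements that leave an earlier start open are age bands and logistics, and none sets a start day. The trial is also described as exploratory, with inference for reference only (Sections 4 and 9.2), and the choice of adjustment could be left to a statistical analysis plan.

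Most of this stands. A start at Visit 1 is the better reading, and a statistical analysis plan can specify the model. It cannot tell a site when to open the powder or make the stool come first; those are conduct instructions that belong in the protocol. The wrong duration is also on the face of this document.

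A reader might go further and infer that the primary formula-arm comparison is biased, or that the treatment effect will be understated because part of it is already present at Visit 1. The documents do not support this. It would need both an enrolment start, which Section 4 does not describe, and subtraction of the Visit 1 value, which 9.7.2 does not specify.

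A reader might also object that the full analysis set in 9.3 requires completion of Visit 1, so an infant randomised earlier who leaves before then is lost. If the planned 20% dropout is assumed to accrue evenly over 360 days, that is at most 0.20 × 28/360 × 160 = 2.5 infants, and none if all are randomised on day 28. Such infants have no stool sample and missing values are not imputed (9.2), so the primary comparison is unchanged.

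**Conclusion.** The point holds as a minor one. The protocol states two durations that differ by 28 days, and the visit window does not reconcile them. The text implies a start at Visit 1 but neither says so nor orders the Visit 1 stool before the first study feed. The possible exposure before that stool is 0 days on the likelier reading and up to 28 days if a site starts at enrolment. The direct test-versus-control comparisons at days 180 and 360 are sound in both cases. What is unsecured is the use of the Visit 1 stool as a baseline.

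This rests on the protocol's text. The flow chart in 6.1 could not be read; if it names a start day, the written sections should be brought into line with it.

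**What to change.** - **Synopsis:** change the intervention cycle from 360 to 332 days.
- **Section 4 and 6.6.1:** state that study powder starts at Visit 1, after the Visit 1 stool has been collected, and that infants randomised earlier keep their usual feeding until then. The formula-feeding minimums written from 0 months should apply to study powder from Visit 1.
- **Section 9.7.2:** compare alpha diversity and SCFAs at days 180 and 360 between the two formula arms, adjusted for the Visit 1 value. That value is already collected, and adjusting for it gives the endpoint's wording a defined meaning.

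The cost is a few sentences, with no extra visit or sample. The real downside is that infants randomised before day 28 have no study exposure in the first month.

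If the sponsor prefers to start at enrolment, the protocol should give the duration as 332–360 days, record the date of the first study feed, and not use Visit 1 as a baseline, either by subtraction or by adjustment.
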